### **7.2.2. Primary Analysis of the Primary Endpoint**

The primary endpoint will be analyzed using Kaplan-Meier survival estimates and associated two-sided 95% confidence interval, using a delayed-entry model controlling for left-truncation of survival times through adjusting for the time from achieving operational tolerance to the time of study enrollment.

A participant will be considered to have lost operational tolerance if they experience rejection, have loss of stable allograft function (in the absence of confounding factors), or restart immunosuppression. The date of loss of operational tolerance (end date of operational tolerance) will be the first date on which the subject meets any of the criteria for loss of operational tolerance. Specifically,

- If tolerance is lost due to rejection, the date will equal the date of the biopsy.
- If tolerance is lost due to restarting immunosuppression, the date will equal the date of the first immunosuppression medication dosage.
- If tolerance is lost due to abnormal allograft function, the date will equal the first recorded abnormal lab date.

The time to loss of operational tolerance for all participants will be evaluated relative to time zero. Time zero will be considered 52 weeks from the participant's last documented dose of immunosuppression and in the absence of rejection or evidence for loss of normal and stable graft function since that last dose. If the exact date of the last dose is not known, the date will be imputed to the 15th of the month when the day is missing, and July 1st when both day and month are missing. The year must be known.

$$\begin{aligned} & \text{time to loss of operational tolerance} \\ & \quad = \text{end date of operational tolerance} - \text{start date of operational tolerance} \end{aligned}$$

Subjects lost to death, voluntary withdrawal or lost to follow-up will be censored at the time of occurrence of these events. Subjects who were followed until study closure (24MAR2020) without losing tolerance will be censored at the time of their most recent data point.

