### **3.1.2 Enrollment and Accrual**

Enrollment will occur on an ongoing basis through November 1, 2020. There is no upper limit on the number of study participants, but we estimate that approximately 70 participants may be enrolled from former ITN studies and from de novo referrals. Enrollment is defined as the signing of informed consent and will be obtained prior to the initiation of any screening or study mandated procedures. Enrolled participants who do not fulfill eligibility criteria or who do not complete any mechanistic sample collection for any reason will be considered screen failures. Screening values will be considered the participant’s baseline for those who meet all eligibility criteria. If a repeat assessment is needed to confirm eligibility, the repeat value will be considered the participant’s baseline value. There is no upper limit on screen failures.

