## 4. ELIGIBILITY

### 4.1 INCLUSION CRITERIA

Participants must meet *all* of the following criteria to be eligible for this study:

1. Recipient of single organ liver or kidney allograft from a living or deceased donor.
2. At screening, operationally tolerant defined as meeting both of the following criteria:
  - a. Absence of any immunosuppressive therapy for  $\geq$  52 weeks prior to the screening visit.
  - b. No evidence of allograft rejection in the 52 weeks prior to the screening visit, based on the medical history.
3. Normal allograft function (see Study Definitions)  
If the site investigator judges that a participant exhibits stable allograft function despite values outside these criteria, then the participant is eligible if the ITN clinical trial physician/protocol chair, the NIAID medical monitor and a subject matter expert concur.
4. Receiving regular follow-up for a kidney or liver transplant by a local physician. Participants must be willing to allow the study team to contact and share medical information with this local physician.
5. Ability to sign informed consent.

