### 6.1 VISIT WINDOWS

#### 6.1.1 Scheduled Visits

Appendix 1 presents the schedule of events for this trial. Visit 0 must occur within 60 days of enrollment. All other scheduled study visits must occur within  $\pm$ 60 days of the scheduled time point listed in Appendix 1.

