## **6.3 CLINICAL LABORATORY ASSESSMENTS**

These laboratory assessments may be performed at study sites, at local laboratories, or through the central laboratory:

- Hematology – CBC with differential and platelets
- Comprehensive Metabolic Panel (Na, K, Cl, HCO3, BUN, creatinine, calcium, glucose, albumin, total bilirubin, direct bilirubin, GGT, AST, ALT, and alkaline phosphatase)
  - Screening allograft function tests must be obtained in the absence of confounding factors such as dehydration, infection etc. Abnormal test results should be repeated to confirm eligibility after any confounding conditions have resolved.
- Fasting lipid panel
- Urine albumin-creatinine ratio
- Urinalysis (protein, glucose, WBC, and hematuria)

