## 4. ANALYSIS SAMPLES

The analysis sample will be comprised of all enrolled subjects that fulfill eligibility criteria and complete at least one mechanistic sample collection.

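### Delayed entry in the primary Kaplan-Meier opens at consent, but only people later found eligible are analysed, so any gap to the qualifying screening visit cannot contain a loss and lifts the retention curve slightly

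*SAP*

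**What the plan says.** - **Entry to the risk set.** SAP 7.2.2 adjusts for left truncation "through adjusting for the time from achieving operational tolerance to the time of study enrollment". Protocol 9.2.1 has the same rule, and SAP Table 7-2 and SAP 7.5 repeat it for the other time-to-event endpoints.
- **Enrollment.** Protocol 3.1.2: "Enrollment is defined as the signing of informed consent and will be obtained prior to the initiation of any screening or study mandated procedures".
- **Who is analysed.** SAP 4 takes "all enrolled subjects that fulfill eligibility criteria and complete at least one mechanistic sample collection". Everyone else who signed consent is a screen failure (protocol 3.1.2 and 3.1.3).
- **Timing.** Protocol 6.1.1: "Visit 0 must occur within 60 days of enrollment". SAP 7.1.2 repeats this.
- **Eligibility.** Protocol 4.1, criterion 2a: "Absence of any immunosuppressive therapy for" at least 52 weeks before the screening visit. Criterion 2b: "No evidence of allograft rejection in the 52 weeks prior to the screening visit, based on the medical history".
- **Baseline.** Under protocol 3.1.2, screening values are the participant's "baseline for those who meet all eligibility criteria", and a repeat value replaces them where a repeat is needed. Protocol 6.3: "Abnormal test results should be repeated to confirm eligibility after any confounding conditions have resolved". No time limit is given for the repeat.

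**The concern.** A delayed-entry Kaplan-Meier estimate is valid if each person joins the risk set at the moment from which a loss would have been seen and counted. Here a person joins at consent but is kept only on the strength of what is found at a later screening visit. Someone who loses tolerance in between drops out of the analysis altogether. Someone who does not is credited with that time as event-free follow-up. This is immortal time. It enlarges the denominators, adds no events, lowers the apparent hazard and raises the curve.

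The retention curve is the study's primary result, and this bias does not shrink as participants are added. The SAP cannot be read as already using Visit 0. Its section 7.1.2 times Visit 0 from enrollment, and its section 5.1 counts enrolled, screen-failed and accrued people separately.

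**Working it through.** **Step 1. Which losses can occur in the gap?** The primary endpoint has three components.

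| Component | Consent to Visit 0 | Visit 0 to a repeat lab |
|---|---|---|
| Rejection | Impossible in an analysed person: breaches criterion 2b | Possible: the look-back ends at the screening visit |
| Restart of immunosuppression | Impossible: breaches criterion 2a | Possible, for the same reason |
| Loss of stable graft function | Cannot be scored: no baseline value yet | Cannot be scored: the repeat value becomes the baseline |

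The consent-to-Visit 0 interval is therefore event-free for all three components. The wait for a repeat lab is firmly event-free only for graft function.

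**Step 2. Inputs.** From the documents: about 70 participants (protocol 9.3) and a window of 0 to 60 days. There is no stated power, loss rate or event count to reproduce. Assumed, because the documents do not give them: a constant loss hazard h of 0.02, 0.05 or 0.10 per year; consent spread evenly after Time Zero; potential follow-up uniform on (0, 2F) years with F = 2.5; and the distribution of the gap G.

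**Step 3. Large-sample bias.** At time t after Time Zero:

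apparent hazard(t) = h × Q(t) / (M(t) + Q(t))

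Here M(t) = E[min(t, G)] is the event-free part of the risk set. Q(t) = E[I(max(t − G, 0))] is the part truly at risk, with I(u) = ∫₀ᵘ exp(−ha)(1 − a/2F) da.

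Example: h = 0.05, every gap 60 days (G = 60/365.25 = 0.164 years), t = 1. Then M = 0.164 and Q = 0.751, so the apparent hazard is 0.05 × 0.751/0.915 = 0.041.

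Integrating over 5 years and subtracting the true retention exp(−5h) gives the upward bias in percentage points:

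| Gaps | h = 0.02 (true 90.5%) | h = 0.05 (true 77.9%) | h = 0.10 (true 60.7%) |
|---|---|---|---|
| None | 0 | 0 | 0 |
| Half none, half spread over 0-60 days | +0.4 | +0.9 | +1.5 |
| All spread over 0-60 days | +0.8 | +1.8 | +3.0 |
| All exactly 60 days | +1.5 | +3.3 | +5.4 |

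**Step 4. Sensitivity to the assumptions, h = 0.05.**
- Changing F from 1.5 to 4 years moves the 0-60 day figure from +2.06 to +1.74 and the 60-day figure from +3.72 to +3.14.
- Spreading eligibility, rather than consent, evenly from Time Zero gives +1.6 for a mean gap of 30 days and +2.7 for 60 days.
- Much of the bias arises soon after Time Zero. For retention from year 1 to year 6 it is +1.7 with every gap 60 days. A simulation of years 2 to 7 with consent spread over 8 years gave 0.7 (0-60 days) and 1.3 (all 60 days).

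**Step 5. Risk time involved.** True risk time for 70 people is about 161.3 person-years at h = 0.05.
- Mean gap 30 days: 70 × 30/365.25 = 5.7 person-years, and 5.7/(5.7 + 161.3) = 3.4%.
- Gap 60 days: 70 × 60/365.25 = 11.5 person-years, and 11.5/(11.5 + 161.3) = 6.7%.

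**Step 6. Against sampling error.** Simulated cohorts of 70, h = 0.05, gaps spread over 0-60 days, true 5-year retention 77.9%:

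| Entry at | Mean | SD | Root-mean-square error |
|---|---|---|---|
| Consent | 79.7% | 9.8 | √(1.8² + 9.8²) = 10.0 |
| Eligibility | 78.3% | 11.4 | √(0.4² + 11.4²) = 11.4 |

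With entry at eligibility the central 95% of estimates run from 53% to 94%, a half-width of about 20 points. A bias of 1.8 points is under a tenth of that, and 3.3 points about a sixth.

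**The case against.** **The gap may hardly exist.** Appendix 1 puts consent, eligibility, labs and samples under one screening visit, and 60 days is an outer limit. This stands. A reader might infer that every participant carries up to 60 days of immortal time. The documents do not show that, and they give no actual gaps. A gap is more likely with remote screening, where footnote 2 of Appendix 1 requires all criteria except graft function to be met before a sample visit is scheduled.

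**The remedy does not lower total error.** This also stands: Step 6 shows it rising from 10.0 to 11.4 points. However, the smaller spread under consent entry comes from filling the risk sets with time in which nobody could fail. That is no reason to leave the entry date misdefined, but it is a reason to show both curves.

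**Not all of the time to confirmed eligibility is event-free.** A reader might infer that the open-ended wait for a repeat lab is immortal time for the whole endpoint. Criteria 2a and 2b look back from the screening visit, so they do not exclude a rejection or restart after it. Moving entry to the repeat lab could hide a real loss unless such events are listed.

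**The study is exploratory and closed, and dates are coarse.** Protocol 9.4 calls it exploratory, and a last-dose date with day and month missing is set to July 1. These facts limit the importance of the point. They do not make consent the right entry date.

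**Conclusion.** The planned entry date is wrong as defined, and the direction of its effect on the retention curve is upward. At an assumed hazard of 0.05 per year, 5-year retention is overstated by about 0.5 to 2 points for gaps between 0 and 60 days and by about 2.5 to 3.3 points if every gap is 60 days. The overstatement is zero if there is no gap. These sizes rest on assumed hazards, gaps, accrual and follow-up, and the bias is well below sampling error at about 70 participants.

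The same argument covers the rejection endpoint in Table 7-2. For all-cause mortality, the requirement for a mechanistic sample also conditions on survival to the first sample. No claim is made here for the other time-to-event endpoints. The point is worth correcting because it concerns the primary result and the dates are already held. It does not show that the study's conclusions would change.

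**What to change.** 1. In SAP 7.2.2, and for the rejection endpoint in Table 7-2, define delayed entry as the date of the qualifying Visit 0 assessment. Where a repeat lab value becomes the baseline, use the date of that lab. List any rejection or restart between Visit 0 and that lab, so that none is silently dropped.
2. In SAP 7.5, for all-cause mortality, use the first mechanistic sample date if it is later.
3. Report the distribution of the consent-to-entry gap and the numbers at risk along the curve. If the gaps are all zero, saying so settles the matter.
4. Show the consent-entry curve as a sensitivity analysis under SAP 7.2.3, which has a heading but no text in the copy reviewed.
5. Record the change in SAP 10.

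**Cost.** The change needs some SAP wording and one derived date from visit and lab dates already collected, plus the sample date for mortality. No new data are needed: follow-up ended on 24 March 2020, before SAP version 1.0 of 17 July 2020. The statistical price is about 3 to 7% less risk time, thinner early risk sets, a wider interval and somewhat higher total error at this sample size. For that reason the two curves should be presented together.

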## **3.3 STUDY ENDPOINTS**

### **3.3.1 Timing of endpoints and subsets for analysis of endpoints**

Study endpoints for all participants will be evaluated relative to Time Zero. Time Zero will be considered the time that operational tolerance was obtained prior to study entry (see Study Definitions). If the exact date of the last dose is not known, the date will be imputed to the 15th of the month when the day is missing, and July 1st when both day and month are missing. The year must be known.

The following subset analyses will be performed on all study endpoints:

- a. allograft type (i.e.- liver or kidney)
- b. previous ITN study participation or non-ITN study-referral

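### The imputed last-dose date has no upper bound, so Time Zero can fall after screening in a participant who meets the 52-week rule

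*SAP*

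**What the plan says.** SAP 7.2.2 fixes the origin of the primary endpoint: "Time zero will be considered 52 weeks from the participant's last documented dose of immunosuppression". A partial last-dose date becomes the 15th if only the day is unknown, and "July 1st when both day and month are missing". Protocol 3.3.1 gives the same rule and sets the minimum information: "The year must be known". Neither section limits how late the imputed date may be.

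Three other statements bear on this.

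- Inclusion criterion 2a (protocol 4.1) requires "Absence of any immunosuppressive therapy for" at least 52 weeks before the screening visit.
- Protocol 3.3.1 describes the origin as lying before entry: "Time Zero will be considered the time that operational tolerance was obtained prior to study entry".
- The Kaplan-Meier estimate uses delayed entry, "adjusting for the time from achieving operational tolerance to the time of study enrollment". Protocol 3.1.2 defines that enrollment date: "Enrollment is defined as the signing of informed consent and will be obtained prior to the initiation of any screening or study mandated procedures". Under protocol 6.1.1, Visit 0 may follow up to 60 days later.

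SAP 7.2.3, the section for sensitivity analyses of the primary endpoint, is a heading without text.

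**The concern.** Criterion 2a and the description of Time Zero in protocol 3.3.1 both place the true origin at or before screening. A fixed mid-month or mid-year date does not respect that limit. A participant who qualified recently, and whose last dose really fell early in the month or year, can receive an origin later than the screening visit.

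Two consequences follow. The origin is late by up to about six months. And if an event or the censoring date comes before the imputed origin, the duration is negative, and the SAP does not say what to do with it.

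Time Zero is the origin for the primary endpoint, the three secondary clinical endpoints, all-cause mortality and biliary complications. No planned analysis would show how much the curves depend on imputed dates.

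**Working it through.** The plan states no figure to reproduce; this is calendar arithmetic on its rules, with 52 weeks = 364 days.

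**Largest shift** (imputed minus true last dose)

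- Day missing: true date the 1st, imputed the 15th, so +14 days. The other extreme is the 31st, −16 days.
- Year only: true date 1 January, imputed 1 July, so +181 days (+182 in a leap year). The other extreme is 31 December, −183 days.

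Imputed Time Zero falls after screening when the shift exceeds the number of days by which screening follows the true 52-week mark.

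**Examples in which criterion 2a is met**

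| | Year only | Day missing | Year only, near closure |
|---|---|---|---|
| True last dose | 10 Jan 2017 | 1 Mar 2017 | 10 Jan 2019 |
| Screening | 20 Jan 2018 | 5 Mar 2018 | 1 Feb 2020 |
| True days off therapy | 375 | 369 | 387 |
| Imputed last dose | 1 Jul 2017 | 15 Mar 2017 | 1 Jul 2019 |
| Imputed Time Zero | 30 Jun 2018 | 14 Mar 2018 | 29 Jun 2020 |
| Screening minus Time Zero | −161 days | −9 days | −149 days |

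In the third example Time Zero is 97 days after study closure (24 March 2020, SAP 7.2.2). The participant is censored at the most recent data point, so the duration is negative even without an event.

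**How often, for year-only dates.** Assume the true last dose T is uniform over a 365-day year, and the wait W from the true 52-week mark to screening is uniform over 0 to w days. Time Zero is after screening when T + W < 181, so for w of at least 181 the share is 181² / (2 × 365 × w) = 32,761 / (730 w).

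| w | Share of year-only dates |
|---|---|
| 183 days | 24.5% |
| 365 days (1 year) | 12.3% |
| 730 days (2 years) | 6.1% |
| 1,825 days (5 years) | 2.5% |
| 3,650 days (10 years) | 1.2% |

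For day-missing dates, day-by-day enumeration gives 0.95%, 0.19% and 0.09% at 1, 5 and 10 years. Exposure ends about two weeks past the 52-week mark when the day is missing, and about six months past it when only the year is known.

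**Size of the error in affected year-only cases.** Within the region T + W < 181, T and W each average 181/3 ≈ 60 days. The July 1 error is 181 − T, on average about 121 days. If the imputed date is capped at screening minus 364 days, the error is W, on average about 60 days.

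**Entry times.** Criterion 2a counts from screening, but delayed entry counts from consent. With an exact last-dose date, screening on day 364 and consent 60 days earlier, entry is already −60 days. A cap tied to screening therefore does not make every entry time positive.

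**The case against.** The strongest case against is that little is at stake.

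- A negative entry time followed by a positive exit time only means that the participant is at risk from Time Zero. Setting entry to zero is correct handling, so a negative entry does not by itself misstate the early risk set. This stands.
- A reader might infer that software would drop such records. Nothing in the documents says which program is used or how it treats them.
- A reader might also infer that the imputation makes participants ineligible or shows that ineligible people were enrolled. It does not. The rule appears only in endpoint-timing text and is not applied to criterion 2a. The conflict is between an analysis date and what criterion 2a implies about the true date.
- A site that can confirm criterion 2a soon after 52 weeks may well know the month. If sites judged eligibility on the latest possible date, or on the imputed date, Time Zero could not fall after screening. This makes the problem rarer, but the documents require neither practice.
- A negative duration from an event needs an early one. The next scheduled visit is at year 1 ± 60 days, about 305 days after screening at the soonest. An interim rejection, a restart of immunosuppression or a retrospectively collected laboratory value could still qualify, and so could early censoring, as in the third example.
- At waits of one to two years the cap saves about 60 days in 6% to 12% of year-only dates, or roughly 4 to 7 days per year-only participant. July 1 imputation carries a mean absolute error of about 91 days (365/4) in any case.

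These points limit the size. They do not remove the defect: applied as written, the rule can produce an origin that the protocol's own text excludes.

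**Conclusion.** The point holds as a minor but definite fault in the imputation rule. For a participant who meets criterion 2a, imputed Time Zero can fall after screening by up to 14 days (day missing) or 181 to 182 days (year only), and even after study closure. The harm is a shifted origin and possible negative durations.

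The frequencies rest on the assumed uniform dates and waits. The longer waits are plausible, because the protocol sets no upper limit on time off therapy and recruits people who have already completed earlier trials. The number of partial dates is not given. As an illustration only, if 10 of about 70 participants had year-only dates, the 1-year figure means about one person affected and the 5-year figure about a quarter of one. The effect on the primary curve is therefore probably small.

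It would be too strong to attribute all negative entry times to imputation, since the gap between consent and Visit 0 produces them with exact dates as well.

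**What to change.** In SAP 7.2.2, add two sentences:

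1. The imputed last dose is the 15th or July 1, but never later than the screening visit minus 52 weeks and never earlier than the last date on which immunosuppression is documented.
2. Entry times at or below zero are set to zero (at risk from Time Zero), for exact and imputed dates alike.

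The first keeps Time Zero at or before screening. The second is needed because consent may precede Visit 0 by up to 60 days.

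In section 7.2.3, repeat the primary curve twice for participants with partial dates, once with the earliest and once with the latest last-dose date consistent with the recorded month or year and these two bounds. Report how many dates were imputed and how many were capped.

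The cost is two sentences and two reruns of the same program. The change belongs in the SAP: version 1.0 is dated 17 July 2020, after the study closed, so a protocol amendment would add nothing.

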## 4.3 PREMATURE TERMINATION OF A PARTICIPANT FROM THE STUDY

**Withdrawal of consent.** Participants who withdraw consent for further follow-up.

**Investigator decision.** The principal investigator may choose to withdraw a participant from the study for any reason.

**Failure to return.** Participants who do not return for visits and who do not respond to repeated attempts by the site staff to have them return will be considered *lost to follow-up*.

Participants who prematurely terminate from the study will not be replaced.

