### 9.2 ANALYSIS PLAN

#### 9.2.1 Primary Endpoint

The primary endpoint is defined in section 3.3.2.

A confounding factor may prevent measurement of normal and stable allograft function. Participants who return to normal and stable allograft function after resolution of the confounding factor and who otherwise meet the primary endpoint criteria will be adjudicated by a Primary Endpoint Adjudication Committee (see Study Definitions).

The primary endpoint will be analyzed using Kaplan-Meier survival estimates and associated two-sided 95% confidence intervals, using a delayed-entry model controlling for left-truncation of survival times through adjusting for the time from achieving operational tolerance to the time of study enrollment. A participant will be considered to have lost operational tolerance if they experience rejection, have loss of stable allograft function (in the absence of confounding factors), or restart immunosuppression. The date of loss of operational tolerance will be the first date on which the subject meets any of the criteria for loss of operational tolerance. Subjects lost to follow-up will be censored at the time of occurrence of the event causing their loss to follow-up.

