## APPENDIX 1. SCHEDULE OF EVENTS

	Study Visit	Screen	Years (+/- 60 Days)				
			1	2	3	4	5
Visit Number	0	1	2	3	4	5	
General Assessments – Recipient							
Informed Consent	X						
Medical and demographic history including transplant specifics	X						
Contact information for local physician 	X						
Inclusion/exclusion criteria 	X						
HLA and blood typing (if available) 	X						
Concomitant Medications	X	X	X	X	X	X	
Adverse Events	X	X	X	X	X	X	
Clinical outcomes of interest review	X	X	X	X	X	X	
Review of all biopsies since last visit, if applicable		X	X	X	X	X	
Review of all rejection episodes since last visit, if applicable		X	X	X	X	X	
Verify participant has ongoing local follow-up care for transplant		X	X	X	X	X	
General Assessments - Donor							
Donor type	X						
Demographics	X						
HLA and blood typing (if available)	X						
Laboratory Assessments							
Hematology - CBC with differential and platelets 	X	X	X	X	X	X	
Comprehensive Metabolic Panel 	X 	X	X	X	X	X	
Fasting Lipid Panel	X	X	X	X	X	X	
Urine albumin/creatinine ratio	X	X	X	X	X	X	
Urinalysis 	X	X	X	X	X	X	
Mechanistic Assessments							
Frozen PBMC – flow cytometry panel staining	X	X	X	X	X	X	
Frozen PBMC – cellular assays	X	X	X	X	X	X	
Serum – HLA alloantibodies, includes DSA, flow PRA	X	X	X	X	X	X	
Whole blood – RNA gene expression profiling	X	X	X	X	X	X	
Urine pellet – gene expression profiling	X	X	X	X	X	X	
Fecal - microbiome profiling	X	X	X	X	X	X	

 For local clinical care provider who is providing active follow-up care for the participant's single organ liver or kidney allograft.

 Participants who complete their screening visit remotely must meet all eligibility criteria, with the exception of confirmed normal allograft function, prior to scheduling a sample collection visit.

 This is a retrospective collection of data from medical records, or a previous ITN trial if applicable.

 If not completed on the same date as the visit's mechanistic assessment, this assessment must be repeated at the time of the visit's mechanistic collection.

 Includes Na, K, Cl, HCO3, BUN, creatinine, calcium, glucose, albumin, total bilirubin, direct bilirubin, GGT, AST, ALT, and alkaline phosphatase.

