 If there is a 25% increase in the value(s) collected during the scheduled annual visit compared to the participant's baseline value, collect all liver function tests (for liver transplant recipients) or all serum creatinine levels (for kidney transplant recipients) since the last visit.

 Participants with abnormal allograft function tests will have their allograft function retested for confirmation (see section 6.3). Abnormal test results thought to be affected by confounding factors should be repeated once the confounding condition has resolved. If a repeat assessment is needed to confirm eligibility, the repeat value will be considered the participant's baseline value (see section 3.1.2).

 Includes protein, glucose, WBC, and hematuria.

 Not indicated for remote visits.

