### **7.1.2. Assessment Time Windows**

Visit 0 must occur within 60 days of enrollment. Each subsequent visit must occur yearly with a +/- 60-day window.

All data will be included in analyses, regardless of time of assessment.

Furthermore, clinical data and mechanistic specimens that have already been collected from enrolled subjects from previous ITN study participation may be used to supplement the ALLTOL specimens and data, as needed.

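### SAP 7.2.2 censors dropouts at the event but completers at their last data point, so unverified time can count as tolerant; it also dates rejection only at biopsy

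*SAP*

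**What the plan says.** **Censoring.** SAP 7.2.2 has two anchors in one curve. For those who leave: "Subjects lost to death, voluntary withdrawal or lost to follow-up will be censored at the time of occurrence of these events". For those who stay: "Subjects who were followed until study closure (24MAR2020) without losing tolerance will be censored at the time of their most recent data point". Protocol 9.2.1 covers only the first group: "Subjects lost to follow-up will be censored at the time of occurrence of the event causing their loss to follow-up". Protocol 4.3 defines loss to follow-up by behaviour, as "Participants who do not return for visits and who do not respond to repeated attempts by the site staff", and gives it no date.

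**How status is learned.** Visits are yearly, within 60 days either side. From Year 1, each visit in Protocol Appendix 1 includes "Review of all rejection episodes since last visit, if applicable". Interim laboratory values are collected only on a trigger at an attended visit: "If there is a 25% increase in the value(s) collected during the scheduled annual visit". Protocol 5.2 has medications, including immunosuppressants, documented at each visit.

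**Event date.** SAP 7.2.2 first gives a general rule, the earliest date on which any loss criterion is met. Three specific rules follow: the biopsy date for rejection, the first dose for restarted immunosuppression, and the first recorded abnormal value for graft function. SAP 7.2 counts both biopsy-proven and clinical rejection. Protocol 9.2.2 dates loss of tolerance by the diagnosis of rejection where that comes first.

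**The concern.** A participant at risk in a Kaplan-Meier curve should be one whose event would be recorded if it happened. A dropout censored after the last status check adds time at risk during which a loss might never reach the database. The denominator grows, the numerator cannot, and estimated tolerance rises. The closure rule stops the clock at the last data, so the two groups are treated differently in the same curve. The confidence interval does not reflect such a shift.

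The rejection rule is a separate matter. An unbiopsied clinical rejection counts as loss of tolerance, but the specific rule gives it no date, and where diagnosis precedes biopsy it gives the later one. Two analysts could date the same case differently.

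This curve is the only primary-endpoint analysis described. Durability of tolerance is also a stated secondary objective (Protocol 2.2).

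**Working it through.** **Inputs from the documents.** Annual visits, ±60 days; delayed-entry Kaplan-Meier from time zero; about 70 participants (Protocol 9.3). There is no stated loss rate, dropout rate or event count, so no plan figure can be reproduced.

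**Assumptions.** Loss of tolerance 2, 5 or 8% per year; non-return 3, 5 or 10% per year; entry spread over 0-5 years after time zero; follow-up 1-5 years. Losses after a dropout's last attended visit go unseen unless stated otherwise.

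**Step 1: closed form.** Let p be yearly non-return, g the credited gap in years and λ the true loss rate. The loss rate is multiplied by a = (1−p) / ((1−p) + p·g), and the 5-year shift is exp(−5λa) − exp(−5λ). With g = 1 (missed-visit date):

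| Case | λ | p | a | Shift (points) |
|---|---|---|---|---|
| Low | 0.02 | 0.03 | 0.97 | 90.76 − 90.48 = +0.27 (unrounded) |
| Middle | 0.05 | 0.05 | 0.95 | 78.86 − 77.88 = +0.98 |
| High | 0.08 | 0.10 | 0.90 | 69.77 − 67.03 = +2.74 |

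With g = 0, a = 1 and the shift is exactly zero.

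**Step 2: simulation of the design.** Delayed-entry curve at 5 years, SAP rule minus last-assessment rule, in points, under two ways of dating the recorded losses:

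| Case | Dropout date, losses dated at occurrence | Dropout date, losses dated at detecting visit | Missed-visit date, at occurrence | Missed-visit date, at detecting visit |
|---|---|---|---|---|
| Low | +0.16 | +0.11 | +0.28 | +0.20 |
| Middle | +0.56 | +0.38 | +0.98 | +0.73 |
| High | +1.56 | +1.1 | +2.72 | +2.06 |

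The SAP's dating lies between the two. Rejection and restarted immunosuppression have their own dates. A laboratory-based loss takes the first recorded abnormal value, which is often the annual visit but is earlier if interim values were collected.

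**Step 3: sampling error at 70 participants.** For the curve from year 1 to year 5, a slightly different quantity from Step 2, with losses dated at occurrence, the SD is 5.3, 7.7 and 9.1 points (low, middle, high). The missed-visit shifts on that scale are 0.22, 0.83 and 2.33, so 0.22/5.3 = 0.04, 0.83/7.7 = 0.11 and 2.33/9.1 = 0.26 SD. For the dropout date they are 0.12, 0.44 and 1.24, or 0.02, 0.06 and 0.14 SD.

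**Step 4: if some gap events are captured anyway.** Middle case, missed-visit date, losses dated at occurrence; difference from the true value in points:

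| Share captured | SAP rule | Censor at last visit, still count late events | One cut-off for both |
|---|---|---|---|
| 0% | +0.95 | −0.03 | −0.03 |
| 50% | +0.46 | −0.51 | −0.03 |
| 100% | −0.02 | −0.99 | −0.03 |

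Moving the censoring date alone would replace an upward bias with a downward one. Events need the same cut-off.

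**Step 5: rejection date.** For an unbiopsied rejection, the SAP's specific rule gives no date, its general rule gives the first date a criterion is met, and Protocol 9.2.2 gives the diagnosis. For a rejection diagnosed before biopsy, the specific rule gives the later date and the other two the earlier. The documents do not allow the size or direction of the effect to be estimated.

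**The case against.** **The bias depends on a reading that the plan does not require.** If loss to follow-up is dated at the last contact with known status, the effect is zero. This stands, but the plan does not require that reading either.

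**Only one of the three dates is undefined.** A reader might infer that every dropout date is undefined. Death has a date and withdrawal of consent normally does. For those two, the issue is only whether status was verified up to that date.

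**Status may be learned outside visits.** Local physicians may be contacted ("Participants must be willing to allow the study team to contact and share medical information with this local physician"), the adjudication committee can ask for more information, and "All data will be included in analyses, regardless of time of assessment". This stands as a possibility. Collection after dropout is nowhere promised, and Step 4 shows that partial capture shrinks the bias without removing it.

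**The SAP follows the protocol.** For losses to follow-up this is true: SAP 7.2.2 keeps the convention of Protocol 9.2.1. A change is therefore a departure made after study closure and must be recorded.

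**Rejection dating is largely covered.** A reader might infer that unbiopsied rejection has no date rule at all. It does: the general first-date rule applies, and adjudication reviews suspected losses. What remains is a conflict of wording between the specific rule, the general rule and Protocol 9.2.2.

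**Missing sensitivity analyses prove little.** SAP 7.2.3 is a heading without text in the copy supplied. Content may have been lost, so the point does not lean on it.

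**Conclusion.** The inconsistency in SAP 7.2.2 is real and of low severity. Where a censoring date falls after the last status check, unverified time is credited as tolerant, and bias from uncaptured events can only be upward. Under the assumed rates the 5-year shift is about +0.1 to +1.6 points (actual dropout date) or +0.2 to +2.7 points (missed-visit date), with the lower values when losses are dated at the detecting visit.

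A reader might take 2.7 points as a finding or a ceiling. It is neither. It is one corner of an assumed grid, with every loss dated at its true occurrence. A wider grid (15% loss, 15% non-return, one-year gap) gives about +6.0. Nor do the documents support saying that the conclusions would be misleading: Protocol 9.4 calls the study exploratory, no test depends on the curve, and the shift is at most about a quarter of the sampling SD under the 2-8% and 3-10% assumptions.

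The rejection-date conflict is a wording matter between SAP and protocol, with no estimable size.

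**What to change.** In SAP 7.2.2:

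- **(a) One cut-off.** Censor every participant without loss of tolerance at the last date on which tolerance status was ascertained. Use the date of death or withdrawal only where status is documented to that date. Apply the same cut-off to events. The event-date rule can be reported as a sensitivity analysis in 7.2.3.
- **(b) Rejection date.** Use the earlier of diagnosis or biopsy, in line with Protocol 9.2.2.
- **(c) Record.** Enter the change from Protocol 9.2.1 in SAP section 10, which now lists only the eGFR method.

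**Cost.** Two or three sentences, one entry, and a check that a diagnosis date is held for each rejection episode. Under the assumptions above, about 2-15 person-years per 70 participants are given up, leaving 128-160, and the curve is slightly less favourable. The study closed on 24 March 2020 and SAP version 1.0 is dated 17 July 2020, so only the SAP changes.

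**What it does not fix.** Dating laboratory-based losses at the first recorded abnormal value carries its own delay. If every loss were dated at the detecting visit, which is the extreme, the curve under rule (a) would still lie about 2.6, 6.1 and 8.6 points above the true value in the low, middle and high cases. That lag is separate from the censoring rule and larger than the shift described here.
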